# **6.4** Surgical Procedure

After the subject's group is identified, the patient should receive one Hydrus or two iStents for the study eye. The surgical procedure to implant either the Hydrus or iStent devices should be performed according to the manufacturer's Instructions for Use. Surgery may be performed under either local or topical ophthalmic anesthesia.

### 6.5 Perioperative Medication

A topical antibiotic and a topical steroid will be administered after surgery. The following dosing regimen is recommended:

- 1. Moxifloxacin 0.5% (Vigamox® or equivalent), one drop four times per day commencing the day of the procedure and continued for approximately one week postoperatively.
- 2. Prednisolone acetate 1.0% (Pred Forte® or equivalent), one drop four times per day for one week; followed by one drop three times per day for one week; followed by one drop two times per day for one week; followed by one drop once per day for one week, then discontinue.

Medication to treat transient post-operative spikes in IOP resulting from the use of viscoelastic and surgical manipulation may be required in the immediate postoperative period, as described below.

#### 6.6 Study Visits and Examination Schedule

All subjects will participate in defined follow-up visits through 24 months. A Case Report Form (CRF) shall be completed for each scheduled exam. Unscheduled or interim visits should also be recorded using the appropriate CRF.

The procedures associated with each study visit are outlined and summarized in Appendix 1 (Schedule of Events and Procedures).

#### 6.7 Unscheduled Visits

Any visit to the clinical site, other than those specified in the protocol, at which the subject has a complaint regarding the study eye and/or treatment to the study eye is required or changed will be documented as an unscheduled visit. The Investigator and/or qualified investigational staff will perform the procedures necessary to evaluate the study participant at these visits, and will record the visit in the subject's chart and on an interim CRF. No specific testing is required at interim visit.

### 6.8 Postoperative Ocular Hypotensive Medications

Since the implantation procedure involves the use of an ophthalmic viscoelastic agent and post-operative steroids, both of which are known to cause IOP elevation in some cases, use of glaucoma medications in the first month after surgery is expected. The first line hypotensive medication in the immediate post-operative period (0-60 days) should be selected from the beta blocker class (if tolerated) as indicated in the table below. In these cases, additional visits may be performed to assess IOP, and medications discontinued if the patient's IOP allows.

Long term medical therapy (defined as medications prescribed at or after the 90-day visit) may be implemented at the Investigator's discretion in order to maintain a safe IOP.

Patient medication usage (medication class, dose, frequency, and brand, if applicable) will be collected at the time of screening. The medications should be assigned a rank order for the purpose of potential reintroduction. If post-operative IOP increases to an unsafe level, ocular hypotensive medications should be reintroduced one at a time and following the order indicated at screening.

If a medication prescribed in the immediate post-operative period does not match the class indicated on the screening list and is continued to the 3 month visit, then the subject should be switched to the pre-surgical medication class and dose if possible.

Reintroduction of ocular hypotensive medication will be recorded in the appropriate Case Report Form, along with the clinical rationale for the decision to apply medications. A record of all medications added, discontinued or changed will be documented on the appropriate Case Report Form.

Because the use of ocular hypotensive medications to control IOP is a study endpoint, the CRF describing the introduction or discontinuation will be reviewed by the Medical Monitor for appropriateness and consistency across study groups. The Medical Monitor will be masked to the identity of the treatment subject.

# 6.9 Subject Disposition

Subjects may be terminated (exited) from the study early due to:

- Screening failure,
- A threat to the subject's health emerges in the course of following study procedures,
- Inability to continue with the study, and
- Voluntary withdrawal.

Subjects who are terminated due to screening failure will not be followed beyond the date of screening failure. For safety reasons, randomized subjects who are terminated should receive routine clinical follow up until the planned end of the study period. CRF's will not be completed for terminated subjects. Terminated subjects will not be replaced. Notification of a subject's early termination should be made immediately to the sponsor and documented on the appropriate CRF.

Completed subjects are those subjects who have not been terminated from the study prior to completion of follow up.

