# 4.3 Safety Analysis

Safety data (adverse events, visual acuity measurements, perimetry, and ocular health findings based on slit lamp and fundus examinations) will be evaluated using descriptive

statistics. Frequency tabulations of safety outcomes will be performed for 1, 3, 6, 12, 18 and 24-month follow up periods. Safety analysis cohorts will be grouped by actual treatment. The study is not designed to detect differences in safety outcomes.

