#### 7.0 ADVERSE EVENTS

All ocular adverse events (AE) in the study eye must be reported on the adverse event CRF. The Investigator must categorize each AE by degree of harm to the subject (mild, moderate, or severe), and the relationship to study device and implantation procedure (not related, possibly, probably, or definitely). Since there are no aspects of the study that can affect both eyes, only serious adverse events observed in the fellow eye will be captured on the case report form throughout the course of the study.

Ocular conditions or diseases that are chronic but stable and meet the inclusion and exclusion criteria should be recorded on the screening CRF under Ocular History. Changes in any chronic condition or disease that are consistent with natural disease progression are not considered AEs and will not be recorded on an AE CRF.

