# 7.6 Adverse Events Requiring Expedited Reporting

Investigators must report all SAEs to Ivantis within 48 hours of observing or learning of the event. For initial SAE reports, investigators should record all case details that can be gathered within 48 hours on the adverse event CRF. SAEs require expedited reporting to the Sponsor or designee regardless of relationship to the implanted devices.

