# 7.7 Unanticipated Adverse Device Effect

An Unanticipated Adverse Device Effect (UADE) means any serious adverse effect (as defined above) on health or safety or any life-threatening problem or death caused by, or associated with a device, if that effect, problem, or death was not previously identified in nature, severity or degree of incidence in the investigational plan or application (including a supplementary plan or application), or any other unanticipated serious problem associated with a device that relates to the rights, safety, or welfare of subjects.

Any UADE must be reported in writing to the Sponsor within 24 hours of knowledge of that event. The Sponsor will be responsible for informing regulatory authorities and all other Medical Ethics Committees/IRBs and Investigators participating in the study of the UADE.

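### Section 6.9 stops case report forms for terminated randomised subjects who should still be seen in clinic, and leaves it unclear which forms stop

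*Combined protocol and SAP*

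**What the plan says.** Section 6.9 makes two statements about the same people. On care: "For safety reasons, randomized subjects who are terminated should receive routine clinical follow up until the planned end of the study period". On data: CRFs "will not be completed for terminated subjects". It adds that terminated subjects are not replaced, and that notification of a subject's "early termination should be made immediately to the sponsor and documented on the appropriate CRF". Apart from screening failure, the exit reasons listed are an emerging risk to health, being unable to continue, and withdrawing voluntarily.

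Other sections set general recording rules:

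- Section 6.6 calls for a CRF at every scheduled exam.
- Section 6.7 calls for an interim CRF, and defines an unscheduled visit as "Any visit to the clinical site, other than those specified in the protocol, at which the subject has a complaint regarding the study eye", or one where treatment of that eye is needed or altered.
- Section 6.8 puts every change in ocular hypotensive medication on a CRF. The masked Medical Monitor reviews these forms because medication use is an endpoint.
- Section 7.0: "All ocular adverse events (AE) in the study eye must be reported on the adverse event CRF".
- Section 7.6 requires notice of SAEs within 48 hours, and says that "investigators should record all case details that can be gathered within 48 hours on the adverse event CRF".
- Section 7.7: "Any UADE must be reported in writing to the Sponsor within 24 hours of knowledge of that event". It names no CRF.

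The data are needed for the endpoints in Section 3.0. The primary endpoint is IOP of 19 mmHg or less without medication at 12 months. The same composite at 24 months is secondary, and the safety endpoints run to 24 months. Section 4.3 adds: "Frequency tabulations of safety outcomes will be performed for 1, 3, 6, 12, 18 and 24-month follow up periods".

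**The concern.** The plan expects terminated randomised subjects to be examined and then, on its face, declines to record what is found. Consent does not explain this, because the rule covers every exit reason and not only withdrawal of consent. Nor is the sentence limited to screening failures: the sentence before it concerns randomised subjects, and screening failures are not followed at all.

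Two things are at stake. The first is endpoint status for randomised subjects that could have been observed. Even if a missing-data rule assigned a value, an observed one would be better. The second is consistency. One site may close every form at exit, while another keeps reporting adverse events and medication changes under the general rules. The safety tables would then depend partly on how each site read one sentence.

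**Working it through.** There is no planned figure to reproduce, because the point is textual. The check sets the passages side by side.

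**Step 1. Which records does Section 6.9 stop, and does another section keep them?**

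| Record after exit | Section 6.9, read literally | General rule | Exited subjects addressed? |
|---|---|---|---|
| Scheduled exam (IOP, BCVA) | No CRF | 6.6: CRF | No |
| Unscheduled visit | No CRF | 6.7: interim CRF | No |
| Medication change | No CRF | 6.8: CRF | No |
| Study-eye ocular AE | No CRF | 7.0: AE CRF | No |
| SAE details | No CRF | 7.6: AE CRF | No |
| SAE notice, 48 hours | Not a CRF | 7.6 | No |
| UADE report, 24 hours | Not a CRF | 7.7 | No |
| The termination itself | CRF required | 6.9 | Yes |

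Section 6.9 does not hold to its own absolute wording, since it requires a CRF for the termination. For the five kinds of CRF in the upper rows, a specific prohibition meets a general duty, and nothing says which governs.

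**Step 2. What is lost on each reading?**

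- *Strict reading (only the exit form survives).* All later IOP, medication, BCVA and AE records are lost from the CRFs. SAE and UADE notices still reach the sponsor.
- *Lenient reading (visit forms stop; AE and medication forms continue).* Medication changes are kept. So are unplanned ocular re-intervention and BCVA loss of 2 lines or more, because Section 7.3 lists both as adverse events. IOP is still lost: a routine clinic visit after exit is not a scheduled exam under Section 6.6, and no other rule calls for its IOP to be recorded. Since the primary endpoint needs both low IOP and no medication, a medication record alone can show a failure but never a success.

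**Step 3. Which endpoint is affected, by time of exit?**

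- Before month 12: the 12-month primary status and the 24-month status.
- Between months 12 and 24: the 24-month status only, as the 12-month form is already complete.

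**Step 4. Who exits?** Section 2.0 handles lack of response by restarting medication, and Section 6.9 does not list it as a reason to exit, so ordinary non-responders stay under observation. An emerging health risk may be related to outcome, but the documents do not equate it with device failure. After the other two reasons, later data may be unobtainable or depend on consent.

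**Step 5. Size.** The documents give no exit rate. Section 2.0 plans 80 subjects per arm, so one subject is 1/80 = 1.25% of an arm. That is a unit of scale and not an estimate of loss or bias.

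**The case against.** The best defence is that Section 6.9 is a deliberate, specific rule and that a specific rule normally overrides general ones. Section 6.7 speaks of people taking part in the study, and a form that records the exit does not conflict with stopping later forms. On this view the text is coherent, and the complaint is only disagreement with a design choice. It is a fair reading, and it narrows the ambiguity. But it is the reading under which the most data are lost, so it strengthens the case for changing the rule.

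A second defence is that data after exit would be of poor quality. Routine care need not follow the 9 AM, two-reading procedure of Section 6.3, the ETDRS chart in Appendix 1, or the ranked reintroduction of medication in Section 6.8. This stands as a reason to flag such values and test their influence. It is no reason to leave them unrecorded, and adverse event reports do not depend on the tonometry procedure.

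A reader might infer more than the documents support:

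- *That medication, BCVA and re-intervention after exit are certainly lost.* Sections 6.8, 7.0 and 7.3 leave this open, as Step 2 shows.
- *That serious events go unreported after exit.* The SAE and UADE notices do not depend on a CRF and carry no exception for exited subjects.
- *That treatment failures are removed and one device is favoured.* Lack of response is not an exit reason, and nothing shows that exits would differ by arm.
- *That the loss can be sized by counting the late-onset items in Section 7.3.* Section 7.1 presents that list as open-ended examples. A count of items describes the list, not the frequency of events or the data lost.

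**Conclusion.** The point holds as a defect in the data-collection rule, with high confidence in the text. Section 6.9 pairs continued clinic follow-up with no CRFs. Taken literally, it discards 12- and 24-month information on randomised subjects who are seen and willing, and its scope conflicts with five general CRF rules. It should be fixed.

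The effect on the results cannot be stated in size or direction. For the primary endpoint, only subjects who exit before month 12, are seen near that time and agree to data collection could be recovered, and the documents give no basis for their number. A claim of known bias between the arms would go beyond the evidence. The conclusion assumes nothing about how missing outcomes are handled; the available text shows no such rule, and the point does not rest on that.

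**What to change.** Replace the CRF sentence in Section 6.9 with:

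> For randomised subjects who are terminated and have not withdrawn consent to data collection, adverse event (including re-intervention) and ocular medication forms continue through 24 months, and IOP and BCVA from routine follow-up within a pre-stated window around 12 and 24 months are recorded on CRFs. IOP not obtained by the Section 6.3 procedure and BCVA not measured by ETDRS are flagged, and their use is examined in a sensitivity analysis.

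The sponsor should set the width of the window in advance. Section 6.9 should also state which other forms stop at exit, including the interim CRF, and be reconciled with Sections 6.6, 6.7, 6.8, 7.0 and 7.6. The consent pages were not available for this review, so the sponsor should confirm that consent covers data collected after exit.

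The cost is a change of wording and some data entry for terminated subjects who agree. The downside is that some values will be off-procedure, hence the flags and the sensitivity analysis. No protocol visit is added and clinical care is unchanged. The change is best made before exits occur, since unrecorded data may not be recoverable later.

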#### 7.0 ADVERSE EVENTS

All ocular adverse events (AE) in the study eye must be reported on the adverse event CRF. The Investigator must categorize each AE by degree of harm to the subject (mild, moderate, or severe), and the relationship to study device and implantation procedure (not related, possibly, probably, or definitely). Since there are no aspects of the study that can affect both eyes, only serious adverse events observed in the fellow eye will be captured on the case report form throughout the course of the study.

Ocular conditions or diseases that are chronic but stable and meet the inclusion and exclusion criteria should be recorded on the screening CRF under Ocular History. Changes in any chronic condition or disease that are consistent with natural disease progression are not considered AEs and will not be recorded on an AE CRF.

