#### 3.0 STUDY ENDPOINTS

The primary effectiveness endpoint for this study is the proportion subjects with IOP ≤19 mmHg *and* without the use of ocular hypotensive medications at 12 months, as measured by Goldmann tonometry.

Secondary effectiveness endpoints include:

- The proportion of subjects who are are not using ocular hypotensive medications at 12 and 24 months, as measured by Goldmann tonometry
- Mean medication use at 12 and 24 months
- The proportion subjects with IOP ≤19 mmHg *and* without the use of ocular hypotensive medications at 24 months, as measured by Goldmann tonometry

Safety endpoints include:

- Frequency of loss in BCVA of 2 lines or more at 12 and 24 months,
- Slit lamp and fundus examination findings at 12 and 24 months,
- Frequency of complications and adverse events at all follow up periods.

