# 7.3 Postoperative Adverse Events

- Chronic pain in the study eye  $\geq 3$  months postoperative
- Flat anterior chamber with lens/cornea touch or with iridocorneal apposition without lens/cornea touch >1 month postoperative
- Best-corrected visual acuity loss of 2 lines (10 letters) or more on the ETDRS chart compared to baseline values, measured at or after 3 months postoperative
- Hypotony (defined as IOP <6 mmHg) at or after 1 month postoperative
- Maculopathy including hypotonic maculopathy
- PAS with device obstruction
- PAS without device obstruction
- Device migration (dislodgement or movement)
- Wound dehiscence (persistent aqueous leak or fistula formation)
- Inflammation (defined as any inflammation requiring treatment with topical, sub-Tenon's or systemic anti-inflammatory medication) lasting longer than 1 month
- Endophthalmitis
- Persistent hyphema of >2 mm present >1 week postoperative
- Corneal opacification
- Corneal decompensation
- Corneal edema persisting >1 month (mild to moderate corneal edema prior to 1 month postoperative is not considered an adverse event)
- Retinal complications (flap tears, retinal detachment, or proliferative vitreoretinopathy)
- IOP spike (elevated mean IOP ≥10 mmHg above the qualifying baseline mean IOP more than 1 month postoperative)
- Events resulting in an unplanned ocular surgical re-intervention (other than paracentesis to relieve pressure prior to 1 week postoperative)
- Phthisis
- Significant foreign body sensation at or after 3 months postoperative
- A change in C/D ratio of  $\geq 0.3$  units on slit lamp biomicroscopic examination

- A 2-point worsening to 4+ anterior chamber cells or flare at or after 3 months postoperative, not associated with a pre-existing condition
- A 2-point worsening to severe on the slit lamp examination findings (other than cells and flare) at or after 3 months postoperative not associated with a pre-existing condition
- A 2-point worsening of ocular symptoms to severe or very severe at or after 3 months postoperative not associated with a pre-existing condition

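### Sections 7.0 and 7.3 do not agree on whether a threshold change that may be glaucoma progression is recorded as an adverse event

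*Combined protocol and SAP*

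**What the plan says.** Section 7.0 opens with a general capture rule: "All ocular adverse events (AE) in the study eye must be reported on the adverse event CRF". Its second paragraph then takes something out of that rule. Stable chronic eye conditions go on the screening form as history, and later changes in them that are "consistent with natural disease progression are not considered AEs and will not be recorded on an AE CRF".

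Section 7.3 lists anticipated postoperative AEs. Three matter here:

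- "A change in C/D ratio of" at least 0.3 "units on slit lamp biomicroscopic examination"
- "Best-corrected visual acuity loss of 2 lines (10 letters) or more on the ETDRS chart compared to baseline values", measured at 3 months or later
- "IOP spike (elevated mean IOP ≥10 mmHg above the qualifying baseline mean IOP more than 1 month postoperative"

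Section 3.0 makes the AE count a safety endpoint in its own right: "Frequency of complications and adverse events at all follow up periods". Section 4.3 says that safety is analysed descriptively, by treatment actually received.

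**The concern.** Section 5.1 requires a glaucoma diagnosis for entry, so every study eye has a chronic condition to which the exclusion in 7.0 can apply. Disc cupping, loss of acuity and rising pressure are all changes that an investigator could put down to that disease. Under 7.3, crossing the threshold makes the change an AE. Under 7.0, the same change is not an AE if it is thought to be progression, and no AE form is completed.

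Progression is also what inadequate pressure lowering would produce. The exclusion can therefore remove from the AE table some of the events that bear on whether a device is failing. A form that is never filed carries no severity grade and no relatedness category, and it gives a later AE review nothing to examine. Two sites following the same protocol could count the same eye differently.

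**Working it through.** The plan gives no figure on this point, so the check is mainly a comparison of text.

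**1. Does 7.3 itself exempt these events?** Only the three items on 2-point worsening (anterior chamber cells or flare, other slit-lamp findings, ocular symptoms) are limited to changes unconnected with a condition already present. The C/D, BCVA and IOP items carry no such limit. The list applies the exemption selectively, whereas 7.0 applies it to everything.

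**2. Is there a rule of precedence?** None appears in 7.0, in 7.1 (which introduces the list) or in 7.3.

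**3. Who decides, and by what criterion?** Section 7.0 says "The Investigator must categorize each AE by degree of harm to the subject" and by relatedness. That step begins only once something counts as an AE. The prior judgment, whether a change is progression, has no criterion and no named assessor.

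**4. Is the judgment masked?** Section 2.0 calls the trial single masked. Section 6.3 says that the subject is not told the assignment and that personnel are to keep the masking. Section 6.8 masks the Medical Monitor, but the review described there covers medication forms. The operating surgeon must know whether one Hydrus or two iStents went in (6.4), and Appendix 1 schedules gonioscopy of the study eye at every visit from 1 week. The judgment will therefore probably be made by someone who knows the device, but this is an inference.

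**5. What is captured without an AE form?**

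| Event | Measured at scheduled visits (Appendix 1) | Planned safety output other than AEs (3.0, 4.3) |
|---|---|---|
| BCVA loss of 2 lines or more | Yes | Yes, same threshold, at 12 and 24 months |
| C/D change of at least 0.3 | Yes, with the fundus exam | Fundus findings, but no 0.3 threshold |
| IOP at least 10 mmHg above baseline | Yes | None; IOP is not among the safety data named in 4.3 |

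**6. Size.** Input: 80 subjects per arm (2.0). If w subjects in an arm have their only AE withheld, the recorded proportion of subjects with an AE falls by w/80.

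- w = 1: 1/80 = 1.25 percentage points
- w = 2: 2/80 = 2.5 points
- w = 4: 4/80 = 5.0 points

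With w₁ and w₂ withheld in the two arms, the artificial difference is (w₁ − w₂)/80. It is zero if the numbers are equal, although both rates are then too low. The documents give no basis for a value of w.

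**The case against.** The strongest defence is that the measurements survive. BCVA loss and slit-lamp and fundus findings are separate safety endpoints at 12 and 24 months. Section 4.3 also promises frequency tables of safety outcomes at 1, 3, 6, 12, 18 and 24 months, and all three thresholds could be recomputed from scheduled visits. This stands, and it limits the point to the AE tabulation. It does not dispose of the point, because no planned output other than the AE table applies the 0.3 C/D threshold or counts IOP spikes.

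A second defence is that 7.1 presents the list as events associated with glaucoma or cataract surgery, so that 7.0 defines an AE and 7.3 only gives examples. That reading is possible. But the three items are written as thresholds without regard to cause, and the exemption written into other items suggests that its absence here carries meaning. The text does not settle the question.

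A reader might also infer more than the documents support:

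- *That the exclusion could empty the 7.3 list.* Most items, such as endophthalmitis, device migration and wound dehiscence, cannot reasonably be called progression of a chronic disease.
- *That slit-lamp worsening and lens change are caught in the same conflict.* The slit-lamp items already carry an exemption that largely agrees with 7.0, and 7.3 lists no lens event.
- *That an unmasked investigator makes the call.* No section says so, and 6.3 has wording on personnel that points the other way.

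**Conclusion.** The point holds as an unresolved conflict between 7.0 and 7.3 over three named events, and it should be corrected. Its reach is the AE frequency endpoint, where each subject whose only event is withheld costs that arm 1.25 percentage points. This assumes that all 80 subjects per arm are in the denominator. The safety cohorts follow actual treatment, so the true denominators may differ somewhat.

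It would go too far to say that the safety comparison is biased or that harm is understated overall. That would need withholding rates by arm, which the documents do not give, and any assumed split between arms would be pure illustration. Bias in the AE table is possible but not shown. Section 4.3 also says that the trial was not designed to detect safety differences. That lowers the stakes for inference, but a descriptive table still depends on complete counts.

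**What to change.** Add one sentence to 7.0: *Any change in the study eye that meets a criterion in 7.3, including any qualifier written in that criterion, is recorded on the AE CRF whatever its presumed cause; attribution to disease progression is entered under relatedness.*

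The clause on qualifiers keeps the sentence consistent with the three items on 2-point worsening: an event that fails their qualifier does not meet the criterion. The relatedness scale in 7.0 already includes a category for unrelated events, so no new field is needed. Section 7.6 already works this way for serious events, which are reported whatever their relationship to the devices.

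The cost is a few more AE forms and a slightly higher reported AE rate. No visit or examination is added.
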